Target population and sampling

This study will recruit pregnant women from a maternal/child health hospital in Guangzhou city and county. Guangzhou Women and Children Medical Center and Zengcheng Maternal and

Child Health Hospital (now Zengcheng Hospital of Guangzhou Women and Children Medical Center) are two key hospitals for perinatal health and pregnant women. In 2016, Guangzhou Women and Children Medical Center delivered 22,455 infants, the highest delivery volume among the hospitals throughout the city. Additionally, Zengcheng Hospital of Guangzhou Women and Children Medical Center provides prenatal care, delivery care, and other main medical services for pregnant women in Zengcheng district. Given the rich clinical research resources and experience of both hospitals, we have elected to conduct our large-scale randomized controlled clinical trial at these two hospitals.

Inclusion criteria: 1) pregnant women on their first visit to the hospital (regardless of gestational age); 2) aged 18 or above; 3) agree to participate and sign an informed consent. Exclusion criteria: 1) systemic or topical vaginal antibiotics were used within 2 weeks prior to the first perinatal visit; 2) diagnosed adverse pregnancy outcomes at recruitment (e.g., stillbirth); 3) pregnant women who refuse to participate in this study.

Sample size estimation

The sample size calculation was based on the following assumptions: 1, the conservative estimate of prevalence of Chlamydia is around 6% among pregnant women in Guangzhou; 2, our meta-analysis showed that the odd ratio of adverse pregnancy outcomes in infected pregnant women versus non-infected pregnant women was 1.8; 3), assuming a 5% significance level on both sides, with a 80% efficacy test and a 2% loss- to-follow-up rate, in order to demonstrate a significantly lower incidence of adverse pregnancy outcomes in the intervention group than in the control group (estimated at 10%, from preliminary data, unpublished results), the sample size

should be approximately 7,725 for each group with an overall target sample size of 15,450 (when $\beta = 0.8$, the estimated sample size is 15,449).

Alpha	OR	p^2	Power	# of positive samples	Prevalence (%)			Total sample size (include 2% loss-to-follow-up)		
					5	6	8	20,306	16,922	12,691
0.05	1.8	0. 1	0.9	995						
0.05	1.8	0. 1	0.8	757	5	6	8	15449	12874	9656

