* The prevalence of abortion, stillbirth, premature birth, low birth weight, SGA and neonatal deaths was 10.1% in the same cohort recruited by Guangzhou Women's Center for 2012-2017.

Questionnaire and follow-up

We will obtain informed consent from participants. We will inform them of the main purpose of the study and the research process (Annex 1). We will emphasize that participation is completely voluntary. Refusal or withdrawal will not affect medical treatment and health care services at the Center. All information obtained by the research group will be strictly confidential and shall not be shared with any other third parties prior to obtaining consent from the participants. After enrolment, we will conduct a baseline survey with all participants, collect relevant medical history, information, and urine samples. The survey will be carried out by the research staff at the Center. The survey content will be built on the questionnaire that is developed by the birth cohort at the Center. We will obtain information on socio-demographic characteristics, chronic medical history, other acute conditions during the first trimester of pregnancy(diagnosis and treatment), number of pregnancies, prior history of previous caesarean section, history of recurrent miscarriage, prior

history of ectopic pregnancy, history of psychiatric illness (e.g., depression), smoking/drinking habits, and history of second-hand smoke exposure. We will add other questions to collect information about history of sexually transmitted diseases and gynecological diseases (such as cervical surgery), whether or not systemic or topical antibiotics were used within the past one month, drug use, sexual behaviors, sexual partner history both before and during pregnancy, history of falls during pregnancy, previous experience of domestic violence, etc. (Annex 2).

Participant recruitment and randomization

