Our primary outcome is the occurrence of adverse pregnancy-related outcomes between the two groups, which include: 1) stillbirth (the definition of stillbirth in this study will use International Classification of Diseases (ICD-11): death prior to complete expulsion (pregnant ≥ 28 weeks) and death during extraction [17]); 2) Spontaneous abortion (less than 1000gms or less than 28 weeks); 3) Preterm labor (birth fewer than 37 weeks gestational age; Infants born before 28 weeks are considered very early-preterm; 28-32 weeks early-preterm; 32-37 weeks late-preterm. 4) Premature rupture of membranes (prior to onset of labor); 5) Low birth weight (2,499g or less); 6) Small for gestational age (weight below the 10th percentile); and 7) perinatal death.

Secondary Outcomes

The secondary outcomes include: C. trachomatis infection of the newborn, Chlamydial conjunctivitis, and pneumonia in the newborn. Laboratory methods for the diagnosis of neonatal

chlamydial infection include: 1) Detection of *C. trachomatis* by sampling from conjunctival scraps and nasopharyngeal/ pharyngeal posterior through direct fluorescence (DFA); 2) PCR and 3) chlamydia culture.

Common Chlamydia conjunctivitis clinical symptoms and supplementary examinations include eyelid and nasal congestion, or 2) catarrhal or mucopurulent secretions, occurring within 5-14 days after birth. It is possible for exudate adhesions to form pseudomembranes. If treatment is delayed more than two weeks, conjunctival follicles may also form.

Chlamydia pneumonia infection may appear insidiously. However, symptoms will usually appear in 4-12 weeks. Common clinical manifestations include nasal mucus secretion, nasal congestion, intermittent cough, shortness of breath, rales on auscultation. There is usually no fever or change in consciousness. Laboratory examinations may show normal white count but elevated eosinophils; moderate hypoxemia on arterial blood gas; bilateral interstitial markings on chest radiography.

Clinical Data Collection

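### Women enter at any gestational age, so later entrants are not at risk of some primary-outcome components; gestational age at enrolment should be a prespecified covariate and set the denominators for abortion and preterm birth

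*Combined protocol and SAP*

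**What the plan says.** Under Target population and sampling, the protocol includes "pregnant women on their first visit to the hospital (regardless of gestational age"). The only exclusion tied to outcome is "diagnosed adverse pregnancy outcomes at recruitment (e.g., stillbirth"). There is no upper limit on gestational age.

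Under Primary Outcome, the composite has seven components. Two carry a gestational-age limit: "Spontaneous abortion (less than 1000gms or less than 28 weeks") and "Preterm labor (birth fewer than 37 weeks gestational age"). The other five are stillbirth, premature rupture of membranes, low birth weight, small for gestational age and perinatal death.

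Under Sample size estimation, the inputs are "assuming a 5% significance level on both sides, with a 80% efficacy test and a 2% loss- to-follow-up rate", an effect described as "the odd ratio of adverse pregnancy outcomes in infected pregnant women versus non-infected pregnant women was 1.8", and an event rate "estimated at 10%, from preliminary data, unpublished results". The table asks for 757 positive women at 80% power. A note ties the event rate to a cohort at the Center: "The prevalence of abortion, stillbirth, premature birth, low birth weight, SGA and neonatal deaths was 10.1% in the same cohort".

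Under Participant recruitment and randomization, women are allocated 1:1 in blocks of 20 by order of recruitment, with no gestational-age stratum. Gestational age at entry is not named among the baseline items, the clinical data list or the sample-size inputs. The supplied text has no analysis section.

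**The concern.** By the week limits, a woman first seen at 28 weeks or later cannot have a spontaneous abortion, and one first seen at 37 weeks or later cannot have a preterm birth. (The weight alternative of 1000 g leaves a narrow opening for a later loss to be called an abortion.) If the rates of these components are taken over everyone enrolled, women at risk are mixed with women who are not. The rate then depends on when women happened to book.

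The treatment contrast also shrinks with late entry. The intervention arm is tested at enrolment and the control arm after delivery or an adverse outcome, so for a woman enrolled near term the two tests are only weeks apart. The sample size nevertheless gives every positive woman the full odds ratio of 1.8.

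At stake are the precision of the primary comparison and the meaning of two component rates.

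**Working it through.** **The plan's own figure.** 757 / 0.05 / 0.98 = 15,449, which matches the stated total. It uses 5% prevalence although the text states 6%; the 6% entry is 757 / 0.06 / 0.98 = 12,874. The 757 does not reproduce: an odds ratio of 1.8 on 10% gives odds 1.8 × 0.1/0.9 = 0.2, so a rate of 16.67%, and the pooled two-proportion formula for 16.67% vs 10% (two-sided 5%, 80% power) needs 407 per arm, 814 in all.

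**Starting power, before any late entry.** Following the plan, only infected women are compared. With n per arm and p̄ the mean of the two rates:

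power = Φ{ [|p₁ − p₂| − 1.96 √(2p̄(1 − p̄)/n)] / √[(p₁(1 − p₁) + p₂(1 − p₂))/n] }

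- 757 positives, n = 378.5: (0.0667 − 0.0484) / 0.0246 = 0.74, so power is 77.1%.
- 6% prevalence: 15,450 × 0.98 × 0.06 = 908 positives, and power is 84.1%.

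The shortfall from 80% to 77% comes from the 757, not from gestational age.

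**Effect of late entry.** Let g be the share of infected women who enter late. The documents do not give g, nor what happens to such women, so both are assumptions. Four cases:

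- A: no benefit, late entrants at 10% in both arms. Control = (1 − g) × 16.67% + g × 10%; intervention = 10%.
- B: no benefit, late entrants at 16.67% in both arms. Control = 16.67%; intervention = (1 − g) × 10% + g × 16.67%.
- C: late entrants have half the events in both arms. Both rates are multiplied by (1 − g/2).
- D: late entrants get half the absolute benefit (13.33% vs 10%).

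| Positives | g | A | B | C | D |
|---|---|---|---|---|---|
| 757 | 10% | 69.0% | 67.2% | 74.6% | 73.2% |
| 757 | 20% | 59.7% | 56.2% | 72.0% | 69.0% |
| 757 | 30% | 49.7% | 44.9% | 69.2% | 64.5% |
| 908 | 10% | 76.8% | 75.0% | 82.0% | 80.7% |
| 908 | 20% | 67.7% | 64.0% | 79.6% | 76.8% |
| 908 | 30% | 57.1% | 51.9% | 76.9% | 72.4% |

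At g = 10% the range is 67% to 75% with 757 positives and 75% to 82% with 908.

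**Would dropping late entrants from the composite recover power?** With 757 positives and g = 20%, n falls to 0.8 × 378.5 = 302.8 per arm. At 16.67% vs 10% that gives 67.6%. All-women power is 59.7% (A), 56.2% (B), 72.0% (C) or 69.0% (D). Restriction gains in A and B and loses in C and D.

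**The case against.** The strongest case on the other side has five parts.

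- **A reader might infer that power falls below 80% because of late entry.** The documents do not support that. They give no distribution of gestational age at entry. At the stated 6% prevalence the trial starts at 84%, and in case C it is still at 82.0% with 10% late. Five of the seven components remain possible after 37 weeks, so zero benefit is an extreme assumption. This objection stands.
- **A reader might infer that a composite restricted to women enrolled before 37 weeks would restore power.** That depends wholly on what is assumed for late entrants; under cases C and D it costs power. This stands too.
- **The 10% rate may already reflect usual booking times,** because it comes from a cohort at the same Center. The documents do not say when in pregnancy that cohort was recruited. This weakens any claim about the event rate, but not the point that treatment has less time to act in women who enter late.
- **Nothing here is bias.** Gestational age is balanced between arms in expectation, and a screening policy for all pregnant women is properly judged on all women. This stands, and it is why the primary population should not change.
- **There are larger matters.** With no analysis section supplied, no covariate is named, and the questionnaire in Annex 2, which is not in the supplied text, may record gestational age. The power figures also rest on comparing infected women only; if all randomised women are compared (10% vs about 9.61% at 6% prevalence with full cure), power is about 12%. That is a separate and bigger issue. It does not remove this one: recording a value is not a plan to use it, and the denominators of two components remain undefined.

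**Conclusion.** The point holds as one of precision and interpretation. Entry is open at any gestational age, two primary components have gestational-age limits, and the supplied text makes no use of gestational age at entry. These facts come from the protocol and need no assumption.

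The size of any power loss cannot be stated. The ranges above illustrate it and rest on four things: an assumed late share, assumed outcomes in late entrants, the plan's infected-only comparison, and the reading of its inputs as 16.67% vs 10%. The direction is towards less power; whether it drops under 80% is not shown. The change is worth making because it is nearly free and must be written down before outcomes are seen.

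**What to change.** Leave eligibility and the all-women primary population as they are.

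1. Prespecify adjustment of the primary comparison for gestational age at enrolment, for example in bands of under 14, 14–27, 28–36 and 37 or more completed weeks. It is fixed before randomisation and can be derived from the dating that the preterm outcome already requires. State that it will be recorded for every woman.
2. Report spontaneous abortion among women enrolled before 28 weeks and preterm birth among women enrolled before 37 weeks. Say how a loss under 1000 g at 28 weeks or later is classified, since it could meet the definitions of both abortion and stillbirth.
3. State the expected distribution of gestational age at entry. The planned pilot of 200 women could supply it.

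The cost is one more baseline covariate and a few lines of analysis text. The downside is that the two component rates will apply only to women at risk when they enrolled, and the text should say so.

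### The target of 15,450 does not follow from its stated inputs: it uses 5% prevalence, not 6%, and its 757 positives give about 77% power, or 57% if controls are at 10%

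*Combined protocol and SAP*

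**What the plan says.** All of this is in the combined protocol and SAP, section IV (Content), under Sample size estimation.

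- Prevalence: "the conservative estimate of prevalence of Chlamydia is around 6% among pregnant women in Guangzhou".
- Effect: "the odd ratio of adverse pregnancy outcomes in infected pregnant women versus non-infected pregnant women was 1.8".
- Error rates and loss: "assuming a 5% significance level on both sides, with a 80% efficacy test and a 2% loss- to-follow-up rate".
- Event rate: the aim is to show a "significantly lower incidence of adverse pregnancy outcomes in the intervention group than in the control group (estimated at 10%, from preliminary data".
- Result: the sample "should be approximately 7,725 for each group with an overall target sample size of 15,450".

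The table lists 995 positive samples for 90% power and 757 for 80% power, with totals at 5%, 6% and 8% prevalence. The 80% row reads "757 5 6 8 15449 12874 9656". The note below the table says the combined frequency of the listed outcomes "was 10.1% in the same cohort recruited by Guangzhou Women's Center for 2012-2017". The text prints β = 0.8 where the table has a power of 0.8. Neither the formula nor the software is named.

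**The concern.** The text names one prevalence and adopts the total belonging to another. The number of positives, from which every total in the table is scaled, looks too small for the stated test and power. The 10% is assigned in the sentence to the control group, but the odds ratio of 1.8 compares infected with uninfected women, and the table pairs it with 10% as p2. The two readings lead to different comparisons and very different sample sizes.

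What is at stake is the claim of 80% power. Depending on which statements are kept, 15,450 women give anything from about 57% to about 84%, and the plan does not tell a reader which figure applies.

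**Working it through.** **Inputs.** From Sample size estimation: odds ratio 1.8, event rate 10%, two-sided α = 0.05 (z = 1.960), power 80% (z = 0.842), loss 2%. Allocation is 1:1, because the randomization section assigns 10 of each block of 20 to intervention. As in the plan's table, the comparison is among chlamydia-positive women.

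**Step 1: reproduce the plan's totals.** Total = positives / prevalence / 0.98.

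| Row | 5% | 6% | 8% |
|---|---|---|---|
| 757 positives | 15,449 | 12,874 | 9,656 |
| 995 positives | 20,306 | 16,922 | 12,691 |

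All six match the table, so the scaling is sound and the layout has been read correctly. The adopted 15,450 is the 5% column; the 6% named in the text gives 12,874.

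**Step 2: turn the odds ratio into proportions.** The odds at 10% are 0.1/0.9 = 0.1111.

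- Reading A, 10% is the rate in uninfected or treated women: odds 0.1111 × 1.8 = 0.2, so infected controls are at 0.2/1.2 = 16.67%.
- Reading B, 10% is the control-group rate, as the sentence says: odds 0.1111/1.8 = 0.0617, so the intervention arm is at 0.0617/1.0617 = 5.81%.

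**Step 3: positives needed.** Per arm, with p̄ the mean of the two rates:

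n = [1.960·√(2p̄(1−p̄)) + 0.842·√(p₁(1−p₁) + p₂(1−p₂))]² / (p₁−p₂)²

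- A: [1.960 × 0.4807 + 0.842 × 0.4784]² / 0.0667² = 407 per arm, 814 in total.
- B: [1.960 × 0.3816 + 0.842 × 0.3805]² / 0.0419² = 652 per arm, 1,304 in total.

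For A, other standard two-sided methods give totals of 806 (arcsine), 810 (unpooled variance), 832 (log odds ratio) and 874 (continuity correction). None gives 757. Unequal allocation does not explain it either, since the smallest total over any ratio is about 813. The 90% row fails in the same way: A needs 545 per arm, 1,090 in total, against the stated 995.

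Fewer than 757 would be enough with a one-sided test (642) or if 1.8 were a risk ratio (590), but the text specifies a two-sided test and an odds ratio.

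**Step 4: power delivered.** Evaluable positives from 15,450 women are 15,450 × 0.98 × 0.05 = 757 or 15,450 × 0.98 × 0.06 = 908.

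| Positives (both arms) | A: 16.7% vs 10% | B: 10% vs 5.8% |
|---|---|---|
| 757 (5% prevalence) | 77.1% | 56.9% |
| 908 (6% prevalence) | 84.1% | 64.8% |
| 995 (plan's 90% row) | 87.3% | 68.7% |

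**Step 5: women needed for 80% power.** A: 814/0.05/0.98 = 16,612, or 13,844 at 6%. B: 1,304/0.05/0.98 = 26,612, or 22,177 at 6%.

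**Step 6: a possible origin of 757.** Under Reading B, replacing the pooled null variance with the variance at the control rate gives 757.0 per arm at 80% power and 993.1 per arm at 90% (stated: 995). So 757 may be a per-arm count entered as a total. The documents do not confirm this. If it is so, 1,514 positives were meant, or 1,514/0.06/0.98 = about 25,750 women at 6%, which also contradicts 15,450.

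**The case against.** The strongest reply is that the prevalence slip errs on the safe side. It raises the target from 12,874 to 15,450, and sizing at 5% is defensible because the background section gives 4.9% as the low end of prevalence among pregnant women in China. If prevalence is 6% as stated, Reading A gives 84.1% power, above the promised 80%.

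Reading A is also plausible. The odds ratio is defined as infected against uninfected, p2 = 0.1 suits a reference rate, and the 10.1% behind it comes from a general hospital cohort rather than from infected women. On that reading, 757 instead of 814 costs only about 3 points of power, and accepted methods themselves differ. The β label is trivial, since the table's column is headed as power.

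Most of this stands as a limit on the size of the problem. The prevalence mismatch alone does not underpower the trial, and the 57% and 65% figures apply only if controls are at 10%. It does not remove the inconsistency. The plan never says that it used 5% and calls 6% the conservative value. No standard two-sided method tried gives 757. The sentence as written puts the 10% in the control group. The possible per-arm origin of 757 would make the shortfall worse, not better.

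**Conclusion.** The concern holds: the stated prevalence, positives, power and control rate cannot all be true. Two parts are definite. The target is the 5% column under a text that says 6%, and 757 (like 995 for 90% power) is too small for the stated two-sided test, by about 7% against 814 on the more favourable reading. The third part is conditional. If the 10% is the control-group rate, 15,450 women give 56.9% power at 5% prevalence or 64.8% at 6%; if it is the rate in uninfected or treated women, they give 77.1% or 84.1%.

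These figures assume 1:1 allocation among positives, 2% loss, a two-sided normal-approximation test of two proportions, and treatment that removes the whole excess implied by an odds ratio of 1.8.

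**What to change.** Rewrite the sample size statement as one consistent set:

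- Give the prevalence used, which is 5% for 15,450, and the reason if 6% remains the expected value.
- Say which women and which arm the 10% describes, and state the implied rate in the other arm.
- Say whether 757 is a total or a per-arm count, and name the formula or software.
- Replace 757 and 995 with counts that can be reproduced (814 and 1,090 in total for 16.7% against 10%), or keep 15,450 and state the power it delivers: about 77% at 5% prevalence and 84% at 6%, or about 57% and 65% if controls are at 10%.
- Write power = 0.8 in place of β = 0.8.

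If 16.7% against 10% is intended, this is a wording change. The total can stay at 15,450, with slightly less power than claimed at 5% prevalence. If controls are expected at 10%, wording is not enough: the sponsor must either accept and state power of about 57% to 65%, or revisit a target that would need about 22,200 women at 6% prevalence or 26,600 at 5%.

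### The sample-size inputs do not return 757 positive women for 80% power (or 995 for 90%), and the 10% rate given to the control group has no clear owner

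*Combined protocol and SAP*

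**What the plan says.** All the inputs are in the combined protocol and SAP, section IV (Content), under Sample size estimation.

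- **Prevalence:** "the conservative estimate of prevalence of Chlamydia is around 6% among pregnant women in Guangzhou".
- **Effect:** "our meta-analysis showed that the odd ratio of adverse pregnancy outcomes in infected pregnant women versus non-infected pregnant women was 1.8". This compares infected with non-infected women; it is not a treatment effect.
- **Error rates and loss:** "assuming a 5% significance level on both sides, with a 80% efficacy test and a 2% loss- to-follow-up rate".
- **Event rate:** the aim is a lower incidence "in the intervention group than in the control group (estimated at 10%, from preliminary data, unpublished results". By word order the 10% belongs to the control group.
- **Result:** "approximately 7,725 for each group with an overall target sample size of 15,450".

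The table lists alpha 0.05, OR 1.8 and a column headed p^2 with the value 0.1, not labelled by group. It gives 757 positive samples for 80% power and 995 for 90%, then totals at 5%, 6% and 8% prevalence. The starred note after the table gives the apparent source of the rate: "The prevalence of abortion, stillbirth, premature birth, low birth weight, SGA and neonatal deaths was 10.1% in the same cohort". That cohort is not described as restricted to infected women.

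No event rate is stated for infected controls or for treated infected women.

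**The concern.** The table sizes the trial on positive women, so the two rates that matter are those in infected controls and in treated infected women. Only one rate is written. The sentence attaches it to the control group, where the higher rate is expected; the table does not say whose it is. Applying an odds ratio of 1.8 upward from 10% gives a much larger absolute difference than applying it downward, so the required number depends heavily on the direction.

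At stake is the power claim. A reader who takes the sentence literally would treat a null result as coming from an 80%-powered comparison. On that reading the power is well below 80%, and on the other readings the stated 757 still falls somewhat short.

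**Working it through.** **Step 1. Reproduce the plan's totals.** Total = positives / prevalence / (1 − 0.02).

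- 757 / 0.05 / 0.98 = 15,449 and 757 / 0.06 / 0.98 = 12,874, both as in the table.
- So 757 means evaluable positives in both arms together. The target of 15,450 comes from the 5% column, although the text assumes 6%.
- Positives expected from 15,450 women after 2% loss: 15,450 × 0.98 × 0.05 = 757 at 5%, and 15,450 × 0.98 × 0.06 = 908 at 6%.

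**Step 2. Derive the second rate.** The odds at 10% are 0.1/0.9 = 0.1111.

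- Upward: 0.1111 × 1.8 = 0.2, giving 0.2/1.2 = 16.67%.
- Downward: 0.1111 / 1.8 = 0.0617, giving 0.0617/1.0617 = 5.81%.
- If 10% is the average over all control women, solve 0.10 = π·p_inf + (1 − π)·p_non with odds(p_inf) = 1.8 × odds(p_non). At π = 5% this gives 16.16% and 9.68%; at π = 6%, 16.07% and 9.61%. The lower rate is what treated infected women would have if treatment removed the whole excess.

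**Step 3. Required positives.** Two proportions, pooled variance under the null, two-sided 0.05, 1:1 allocation (10 of each block of 20, section IV, Participant recruitment and randomization):

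n per arm = [1.96·√(2·p̄·(1−p̄)) + z·√(p1(1−p1) + p2(1−p2))]² / (p1 − p2)², where p̄ is the mean of the two rates and z = 0.842 for 80% power.

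- 16.67% vs 10%: (0.9422 + 0.4027)² / 0.06667² = 406.96 per arm, so 814 in total.
- 10% vs 5.81%: (0.7480 + 0.3202)² / 0.04186² = 651.15 per arm, so 1,303 in total.

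For 90% power (z = 1.282) the same formula gives 544.3 and 871.2 per arm, so 1,089 and 1,743 in total. The table has 995.

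**Step 4. Power.** Power = Φ{[|p1 − p2|·√n − 1.96·√(2·p̄·(1−p̄))] / √(p1(1−p1) + p2(1−p2))}, with n = 378.5 per arm (757 positives) or 454.2 per arm (908 positives).

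| Whose rate is 10%? | Rates among positives | Positives for 80% | Power at 757 | Power at 908 |
|---|---|---|---|---|
| Treated (or non-infected) women | 16.7% vs 10% | 814 | 77% | 84% |
| Infected controls | 10% vs 5.8% | 1,303 | 57% | 65% |
| All control women | about 16.1% vs 9.6–9.7% | 837–842 | 76% | 83% |

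Because the target was set from the 5% column, the 757 and 908 columns are also the power of the planned 15,450 women at 5% and 6% prevalence.

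**Step 5. Could another formula explain 757?** For 16.7% vs 10% at 80% power, the unpooled version gives 808, log odds ratio 832, arcsine 804 and continuity-corrected 874. For 10% vs 5.8% the range is 1,283 to 1,398. No two-sided, equal-allocation variant tried returned both 757 and 995 from these inputs. A continuity-corrected formula would need an odds ratio near 1.875 at 10%, or a base rate near 12%.

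**The case against.** The strongest reply is that the sentence is a translated parenthetical and may simply give a background incidence. The starred note supports this: its 10.1% comes from a general hospital cohort. The table's odds ratio compares infected with non-infected women, so 0.1 fits naturally as the non-infected reference rate. On either of those readings, 15,450 women at the stated 6% prevalence give 83% to 84% power. Even 5.4% prevalence would yield the 814 positives needed for 16.7% vs 10% (814 / (15,450 × 0.98) = 5.4%). This stands, and it is why the point is about the stated figures rather than the size of the trial.

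Three stronger inferences are tempting, and the documents do not support them.

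- *The sample size works only if 10% is the treated rate.* That reading comes much closer than 10% vs 5.8%, but it needs 814, not 757. The sponsor's formula is unknown, and 16.7% and 5.8% appear nowhere in the plan.
- *A 10% control rate can never give 80% power.* If it is the rate in all control women, power among positives is about 83% at 6% prevalence.
- *Power is only about 10% to 12%, because all randomised women would be compared.* That figure concerns the choice of analysis population. It says nothing about which group the 10% belongs to.

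The reply does not rescue the figure of 757 positives for 80% power, which none of the three readings returns.

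**Conclusion.** The stated 757 positives for 80% power and 995 for 90% do not follow from the stated inputs in either direction of the odds ratio. The shortfall at 757 is small if 10% is the lower rate (77%) or the rate in all control women (76%). It is large if 10% is the infected-control rate, as the sentence can literally be read (57%, or 65% with 908 positives).

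The documents do not establish which reading was intended, so a reader should not infer that the trial is underpowered or that the rate was certainly given to the wrong group. These results assume a two-sided 5% test, equal arms, a comparison among chlamydia-positive women, and treatment that removes the full excess implied by the odds ratio of 1.8. The plan does not state that last assumption. The point calls for a correction to the sample-size figures; it is not a must-fix.

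**What to change.** In section IV, Sample size estimation, the sponsor should confirm which reading was intended and then:

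1. State which women the 10% describes, label the p^2 column accordingly, and say how the rate relates to the 10.1% cohort figure.
2. Write out both event rates used, and say that the comparison is among chlamydia-positive women.
3. State the assumption that treatment removes the whole excess implied by the odds ratio of 1.8.
4. Replace the figures for 80% and 90% power with recalculated ones for the chosen reading, naming the formula.
5. Give the power of the planned 15,450 women at both 5% and 6% prevalence: 77% and 84% for 16.7% vs 10%; 57% and 65% for 10% vs 5.8%; 76% and 83% if 10% is the rate in all control women.

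The cost is a rewritten paragraph and table. No extra women are proposed. At 5% prevalence the stated power becomes less favourable on every reading; at 6% it stays above 80% on two of the three.
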